The number and percentage of patients with a microbiologic success at the Day 12 (+/-1 day) visit will be determined. The validity of the urine dipstick as a screening tool to identify patients with a positive urine culture will be evaluated by calculating the percentage of patients with both a positive nitrite test and a positive test for pyuria on dipstick/urinalysis, who have $\geq 10^5$ CFU/ml of a uropathogen isolated from urine culture. Safety analyses will be conducted in all patients who receive any amount of ciprofloxacin. Safety will be assessed through summaries of AEs.

Date of Original Approved Protocol: September 29, 2017

Date of Most Recent Protocol Amendment (if applicable): March 27, 2018

TABLE OF CONTENTS

SYN	NOPSIS	2
LIST	T OF APPENDICES	13
LIST	T OF ABBREVIATIONS AND DEFINITIONS OF TERMS	14
1	INTRODUCTION	17
1	1.1 Indication	17
1	1.2 Background and Rationale	17
	1.2.1 Rationale for Study	17
	1.2.2 Dose Rationale	18
2	STUDY OBJECTIVES	18
2	2.1 Objectives	18
3	STUDY DESIGN	19
3	3.1 Investigational Study Medications	19
3	3.2 Adjunctive Systemic Antibiotics	19
3	3.3 Additional, Non-Study Therapy Antibiotics	20
4	STUDY POPULATION SELECTION	20
4	4.1 Inclusion Criteria	20
4	4.2 Exclusion Criteria	21
4	4.3 Enrollment Criteria	22
4	4.4 Women of Child-Bearing Potential	22
5	STUDY TREATMENTS	23
5	5.1 Allocation to Treatment	23
5	5.2 Drug Supplies	23
	5.2.1 Formulation and Packaging	23

	5.2.2	Preparation and Dispensing	24
	5.2.3	Compliance	24
	5.3 Dr	ug Storage and Drug Accountability	24
	5.4 Me	edication(s), Adjunctive Therapy and Non-drug Therapy	25
	5.4.1	Concomitant Medications	25
	5.4.2	Concomitant Antibacterial Medications	25
	5.4.3	Non-drug Adjunctive Therapy	25
6	STUDY	PROCEDURES	26
	6.1 Sci	reening (Day 1)	26
	6.2 Tre	eatment Period	26
	6.2.1	Baseline (Day 1)	26
	6.2.2	End Of Treatment (EOT) Day 3 or 4 (+1 day)	27
	6.3 Fo	llow-up Period	27
	6.3.1	Test of Cure (TOC) Day 12 (+/- 1 day)	27
	6.3.2	Post Test of Cure (TOC) Day 21 (+/- 3 days)	28
	6.4 Pat	tient Withdrawal from Treatment or Study	28
7	ASSESS	MENTS	28
	7.1 Sa	fety	28
	7.1.1	Clinical Laboratory Assays	28
	7.2 Eff	ficacy	29
	7.2.1	Overall Response	29
	7.2.2	Microbiologic	29
	7.2.3	Investigator-Determined Clinical Response	30
	7.2.4	Other Assessments	31

8	ADV	ERSE EVENT REPORTING	31
	8.1	Adverse Events	31
	8.2	Reporting Period.	31
	8.3	Definition of an AE	32
	8.4	Abnormal Test Findings	33
	8.5	SAEs	33
	8.6	Hospitalization	34
	8.7	Severity Assessment	35

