Appendix 5 Summary of Changes

This summary of changes provides an overview of substantive changes and additions made for protocol IT-004-401 amendments. In addition, minor editorial revisions have been made for consistency.

General

• All Pages: Header

From: Amendment 01:08 November 2017 To: Amendment 02:27 March 2018

Study Procedures

- Section 4, 4.1-3, 4.1-4: clarification of; study population requirement of positive for both leukocyte esterase and nitrite dipstick, midstream specimen for diagnosis, informed consent process
- Section 5.2-1, 5.2-3: removal of additional language that does not apply to this study, clarification of site to collect at least the day and time of patients first dose taken during treatment follow up.
- Section 6.1: updated language to align with revisions to Section 4.
- Section 6.3.2: added requirement for Post Test of Cure (TOC) Day 21 (+/- 3 days) follow up call
- Section 9.2-5: clarified outcome assessment language
- Appendix 1 Schedule of Activities: Post Test of Cure (TOC) Day 21 (+/- 3 days) follow up call added
- Appendix 2 Microbiology: removed reference to requirement of long term storage of specimen at local lab
- Appendix 3: Revised Patient Assessment Symptom Questionnaire

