5.3 Additional Efficacy Outcomes Measures

Microbiologic response

Microbiologic response is assessed on Day 3 or 4 (+1 day) EOT and Day 12 (+/- 1 day) TOC in the ITT, m-MITT, CE-EOT, CE-TOC, ME-EOT and ME-TOC populations.

Microbiological	Definition
response	
Eradication	A urine culture taken at baseline and compared with the culture
	from the Day 3 (+1 day) (EOT) visit or Day 12 (+/- 1 day)
	(TOC) visit showed that the urine culture obtained at the
	relevant visit demonstrated <10 ³ CFU/mL of the original
	uropathogen.
Persistence	Uropathogen present at baseline grew at ≥10 ³ CFU/mL at the
	time-point of analysis, i.e. EOT or TOC.
Indeterminate	Patient was lost to follow-up or an assessment was not
	undertaken such that no urine culture was obtained (or culture
	results could not be interpreted for any reason) at either the
	EOT or the TOC visit.

• Clinical response:

Clinical response (done programmatically) will use the definitions below to document response at Day 3 or Day 4 (+ 1 day) (EOT), Day 12 (+/- 1 day) (TOC) and Day 21 in the ITT, m-MITT, CE-EOT, CE-TOC, ME-EOT and ME-TOC populations.

Clinical response	Definition
Clinical cure	All pre-therapy signs and symptoms of the index infection had resolved such that no additional antibiotics were required
Clinical failure	Patients who met any one of the criteria below were considered as failure:
	Death related to uUTI prior to Day 3 or Day 12 or Day 21 respectively
	No apparent response to treatment; persistence or progression of most or all pre-therapy signs and symptoms or use of additional antibiotics for the current infection
	Patient previously met criteria for failure and received rescue antibiotics
Indeterminate	Study data were not available for evaluation of efficacy for any reason, including:
	Patient lost to follow-up or assessment not undertaken such that a determination of clinical response could not be made at either the EOT or TOC visit
	Death prior to Day 3 or Day 12 or Day 21, respectively, where uUTI was clearly noncontributory

In addition to the clinical response above, following sensitivity analyses will be performed on Day 12 (+/- 1 day) in the m-MITT population,

- Sensitivity Analysis 1: Will follow the same definition of clinical response defined in section 5.3 except, urgency is excluded and considering all other symptoms are resolved and no new uUTI symptoms.

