6.5 Handling of Missing Data

Missing data will be handled as outlined below: Confidential Page 12

 All missing and partial dates for events and assessments occurring after start of enrollment or for medications received after start of enrollment will be queried for a value. If no value can be obtained, substitutions will be made as follows:

- For start dates, missing months and days will be defined by "01", as long as this occurs on or after the first dose of study drug. If the algorithm produces a date prior to the first dose of study drug, the date of the first dose of study drug will be used for the partial date. For stop dates, missing months will be defined as "12" and days will be defined by the last day of the respective month. These substitutions will be used in calculations; however, the actual value recorded on the e-CRF will be used for all listings.
- The intensity and causality assessment for an AE cannot be missing. Missing data will be queried for a value. If no value can be obtained, worst possible scenario will be considered. For example, missing intensity will be considered as 'severe' and missing causality will be considered as 'treatment related'.

For efficacy response, missing data will be handled as follows:

- For any outcome measure,
 - Patients will be defined as an indeterminate at any outcome measure (overall or clinical or microbiological) if any data needed to determine the outcome of a patient is missing. For example, if the assessment of the symptoms was not completed at EOT, for any reason, the patient will be considered an indeterminate response. By definition, patients with an indeterminate response are included in the denominator for analyses in the ITT and m-mITT populations, and are considered failures.
- For the Investigator's assessment of clinical response at EOT and TOC
 - Patients will be considered an indeterminate response if data are not available for the evaluation of efficacy at EOT and TOC for any reason.
- Except as specifically noted for preplanned imputation analyses, missing values for other individual data points (not described above) will remain as missing. Missing values will not be imputed and only observed values will be used in data analyses and presentations.
- Where individual data points are missing, categorical data will be summarized based on reduced denominators (i.e., only patients with available data will be included in the denominators).

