8 DIFFERENCES WITH ANALYSES SPECIFIED IN THE PROTOCOL

- The clinical evaluability rules in the protocol have been modified in the SAP (section 4.5). The prior antibiotic rule was dropped because it is an exclusion criterion in the protocol and applicable to all patients. The requirement that a study entry urine culture obtained before ciprofloxacin administration was dropped since the clinical evaluability rules should only be related to clinical data, not microbiological data.
- The primary efficacy outcome measure in the SAP (section 5.1) was further clarified by adding the rules for non-responder.
- Analyses were added to the SAP (section 5.3) for day 21 even though they weren't listed in the protocol.
- The rule, 'patient previously met criteria for failure', in the protocol for clinical response was modified in the SAP (section 5.3) to 'patient previously met criteria for failure and received rescue antibiotics' to specify the rule more precisely.

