Appendix 2 - Patient Symptom Assessment Questionnaire (PSAQ)

UTI symptoms	Symptom assessment
Gross hematuria	No symptom
	Mild
	Moderate
	Severe
Pain or uncomfortable pressure in the lower abdomen/pelvic area	No symptom
	Mild
	Moderate
	Severe
Pain or burning when passing urine	No symptom
	Mild
	Moderate
	Severe
Frequency of urination or going to the toilet very often	No symptom
	Mild
	Moderate
	Severe
Urgency of urination or a strong and uncontrollable urge to pass urine	No symptom
	Mild
	Moderate
	Severe

New Patient Symptom Assessment Questionnaire (PSAQ)

INSTRUCTIONS: Do you have any of the following symptoms due to your current UTI? If yes, indicate severity by checking Mild, Moderate or Severe. If you do not have a symptom, or if a symptom is present but related to another known condition, then check No Symptom.

CHECK ONLY ONE RESPONSE PER QUESTION, REFER TO PAGE 2 FOR GUIDANCE SPECIFIC TO QUESTIONS 2 AND 4.

	Severity (check one)			k one)	Complete the below on DAY 12 if you still have symptoms.	
	Mild	Moderate	Severe	No symptom/ Resolved or returned to the same condition as before you had a UTI	Question: What is the impact of your remaining symptom(s) on your daily activities (i.e., how bothersome are the symptoms)?	
Gross hematuria (visible blood in your urine)					☐ Not at all ☐ Not significantly bothersome ☐ Moderately bothersome ☐ Severely bothersome	
Pain (uncomfortable pressure) in the lower abdomen/pelvic area*					☐ Not at all ☐ Not significantly bothersome ☐ Moderately bothersome ☐ Severely bothersome	
Burning (dysuria) when passing urine					☐ Not at all ☐ Not significantly bothersome ☐ Moderately bothersome ☐ Severely bothersome	
Frequency, urgency of urination or going to the toilet very often**					☐ Not at all ☐ Not significantly bothersome ☐ Moderately bothersome ☐ Severely bothersome	

ADDITIONAL GUIDANCE FOR QUESTIONS 2 AND 4

* Pain	(uncomfortable	pressure)	in the	lower
abdom	en/pelvic area			

- Choose "No symptom" if no significant pain or back to before you had a UTI
- · Choose "Mild" if occasional pain, but usually overlooked
- · Choose "Moderate" if considerable pain, but tolerable
- · Choose "Severe" if severe pain requiring treatment

- Choose "No symptom" if you can hold your urine for more than two hours during the daytime, or you can hold your urine as long as you could before you had a UTI
- Choose "Mild" if more frequent than normal, but can hold your urine for 1-2 hours

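### Day 21 clinical response has no rule for women never due the Day 21 call, and the natural reading of SAP 6.5 counts them as failures in ITT and m-MITT

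*SAP*

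**What the plan says.** The summary of changes in Protocol Appendix 5 covers one step, "From: Amendment 01:08 November 2017 To: Amendment 02:27 March 2018", and lists for Section 6.3.2 an "added requirement for Post Test of Cure (TOC) Day 21 (+/- 3 days) follow up call". The synopsis gives "Date of Original Approved Protocol: September 29, 2017". In Protocol 6.3.2 and Appendix 1 the telephone call is the only contact at Day 21, and Protocol 13.1 still ends the study at the TOC visit.

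SAP 5.3 defines a programmatic clinical response of cure, failure or indeterminate. Its list of time points and populations ends "TOC) and Day 21 in the ITT, m-MITT, CE-EOT, CE-TOC, ME-EOT and ME-TOC populations", with no restriction by protocol version. ITT is everyone enrolled (SAP 4.1).

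SAP 6.5 makes a patient indeterminate on any outcome measure when data needed to determine that outcome are missing. Such patients are "included in the denominator for analyses in the ITT and m-mITT populations, and are considered failures".

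SAP 8 records that "Analyses were added to the SAP (section 5.3) for day 21" although the protocol did not list them. It does not say what happens to women for whom no call was planned.

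**The concern.** A woman whose follow-up ended before Amendment 02 took effect has no Day 21 data by design. That is different from a call that was due and missed. The SAP does not separate the two, and its missing-data rule turns the first into a failure. The Day 21 cure percentage would then depend partly on the enrolment calendar, and the error has only one direction, downward. A reader comparing the Day 12 and Day 21 cure percentages in m-MITT would be comparing figures in which part of the fall may have nothing to do with the patients' symptoms.

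**Working it through.** **Were any women assessed before Amendment 02?** Neither document gives a first-enrolment date or a count, so this is an inference from four places:

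- Appendix 5 of the protocol lists a revision of the symptom questionnaire in the same amendment that added the call.
- The amended form in Protocol Appendix 3 has four items and merges frequency with urgency.
- SAP Appendix 2 prints a five-item form with frequency and urgency separate, followed by one headed "New Patient Symptom Assessment Questionnaire (PSAQ".
- SAP 7.2 summarises the two symptoms separately, and Sensitivity Analyses 1 and 2 in SAP 5.1.1 each drop one and keep the other. The merged item cannot supply that.

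The SAP (30 July 2019) therefore appears to expect data from the earlier form.

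**Which part of SAP 6.5 governs?** The outcome rule covers any outcome measure, including clinical response. A later bullet allows reduced denominators where individual data points are missing. It follows a bullet confined to data points not already dealt with, but carries no such limit itself. The specific outcome rule is the more natural one to apply, though the text leaves room for doubt.

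**Size.** The plan states no Day 21 rate, so there is no figure to reproduce. Inputs:

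- Expected m-MITT: 250 − 50 = 200 (SAP 6.1).
- c, the Day 21 cure rate: assumed 75%, taken as the same in women due and not due a call.
- f, the share never due a call: assumed, shown as a range.
- Every woman due a call is reached, so that only this effect is shown.

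Reported rate = c × (1 − f). Fall = c × f. The yardstick is SE = √(0.75 × 0.25 / 200) = 3.06 points.

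| f | Women not due, of 200 | Reported rate | Fall (points) | Fall / SE |
|---|---|---|---|---|
| 5% | 10 | 71.3% | 3.75 | 1.2 |
| 10% | 20 | 67.5% | 7.5 | 2.4 |
| 20% | 40 | 60.0% | 15.0 | 4.9 |
| 30% | 60 | 52.5% | 22.5 | 7.3 |

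At f = 2% (4 women) the fall is 0.75 × 2 = 1.5 points, about half an SE. The choice of c matters less than f: at f = 10% the fall is 7.0 points for c = 70% and 9.0 for c = 90%. Women not due a call who would have failed anyway add nothing to the fall, because c × f counts only would-be cures.

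**With the denominator limited to women due a call**, at f = 20%: cures = 0.75 × 160 = 120. The rate is 120/160 = 75.0%, against 120/200 = 60.0% as written. SE = √(0.75 × 0.25 / 160) = 3.42 points.

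**CE and ME.** Membership depends on EOT or TOC data (SAP 4.5, 4.6), so a woman can be in either population and have no Day 21 data. The SAP 5.1 formula without an indeterminate term is written for overall response and assumes sufficient information, which membership does not guarantee at Day 21.

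**The case against.** Four objections have weight.

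First, the affected women are inferred. Two undated forms do not prove that anyone's Day 21 window had passed before the call took effect, since a woman could complete the old form at entry and still be called. This stands: f is unknown and could be small. It does not remove the need for a rule.

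Second, the SAP does not say outright that a call never scheduled counts as missing data. The indeterminate definition in SAP 5.3 names only EOT and TOC for an assessment not done, and the example in SAP 6.5 is an EOT assessment. This stands as a reason to speak of the natural reading. However, the definition covers data unavailable for any reason, and SAP 6.5 covers any outcome measure.

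Third, a reader might infer that the lower Day 21 rate would be taken for relapse. The documents do not support going that far. SAP 7.6 plans counts and percentages for each category, and reasons for indeterminate status for most endpoints, so absent calls would probably be visible as their own row. The cure percentage would still carry them in its denominator.

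Fourth, a reader might infer that indeterminates drop out of CE and ME at Day 21, so that those populations would disagree with m-MITT. That is not established, because the Day 21 rule there is undefined.

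**Conclusion.** The concern holds as a gap in the rule that, applied on its natural reading, lowers the Day 21 cure percentage in ITT and m-MITT by about c × f. That is 7 to 9 points for each 10% of women never due a call, for c between 70% and 90%. Both c and f are assumptions. That f exceeds zero is a strong inference from the two questionnaires, but it is not documented; if f is zero, nothing changes. Day 21 clinical response is an additional, descriptive outcome, and the Day 12 primary outcome is untouched. The point should be corrected, but it does not threaten the trial's main result.

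**What to change.** In SAP 5.3 and 6.5:

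- Limit the Day 21 denominator in every population to women due a Day 21 call. Define this by whether Amendment 02 was in force at the woman's site when her window opened (Day 21 − 3 = Day 18), and not by her outcome or by whether a call was made.
- Exclude women not due a call whatever their earlier outcome. Keeping only their known failures would bring back the downward bias.
- Report their number as not scheduled, separately from indeterminate.
- Count as indeterminate, and so as failure, only a due call that was missed.
- State how Day 21 indeterminates are treated in CE and ME.
- Show Day 12 response in the same subset, so that any change is within the same women.

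The cost is SAP wording and one derived flag. The flag needs the date Amendment 02 took effect at each site, and neither document shows that this is collected. The Day 21 denominator shrinks: at f = 20% the SE rises from about 3.1 to 3.4 points.

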6.6 Comments on Statistical Analysis

The following general comments apply to all statistical analyses and data presentations:

- Summaries will include frequency and percentages for categorical data; frequency and median for ordinal data; and number, mean, standard deviation, and median, minimum and maximum for continuous data.
- Duration variables will be calculated using the general formula: (end date start date) +1 for end dates after first dose and (end date start date) for end dates before first dose.
- If the reported value of a clinical laboratory parameter cannot be used in a statistical summary table (e.g., a character string is reported for a parameter of the numerical type),

a coded value must be appropriately determined and used in the statistical analyses. In general, a value or lower and upper limit of normal range such as '<10' or ' \leq 5' will be treated as '10' or '5' respectively, and a value such as '>100' will be treated as '100'. However, the actual values as reported in the database will be presented in data listings.

- Individual patient listings of all data represented on the eCRFs will be provided to facilitate the investigation of tabulated values and to allow for the clinical review of all efficacy and safety parameters.
- Version 9.4 of SAS® statistical software package will be used to provide all summaries, listings, graphs, and statistical analyses.

7 STATISTICAL ANALYSES

7.1 Patient Disposition

The number of patients included in each of the study populations (i.e.: ITT, Safety, MITT, m-MITT, CE-EOT, CE-TOC, ME-EOT and ME-TOC) will be summarized by ciprofloxacin-susceptible, ciprofloxacin-non-susceptible, other (Includes patients with no pathogen or contaminated urine sample at baseline) and total (includes all patients). A listing will be provided that details each patient's inclusion in and exclusion from each analysis population and the reasons the patient is excluded from the population(s).

- The frequency and percentage of patients completing the study, prematurely discontinuing from the study will be presented for the ITT, MITT, m-MITT, CE-EOT, CE-TOC, ME-EOT and ME-TOC populations.
- Reasons for premature withdrawal from the study as recorded on the e-CRF will be summarized (frequency and percentage).
- A listing of all patients who prematurely withdrew from the study will be presented, and the primary reason for premature withdrawal from the study will be provided.
- A listing of death will be presented separately.

7.2 Demographics and Baseline Characteristics

Demographic data and baseline characteristics will be presented for the ITT, Safety, m-MITT, CE and ME populations. A table as well as a listing will present the patient demographics [e.g., age, height, weight, BMI and race] and baseline characteristics (height, weight, as a continuous variable). Age will be calculated from the date of birth to the date demographics were collected.

The UTI symptoms (gross hematuria, pain or uncomfortable pressure in the lower abdomen/pelvic area, pain or burning when passing urine, frequency of urination or going to the toilet very often, urgency of urination or a strong and uncomfortable urge to pass urine) will be summarized.

Pathogens at baseline will be summarized as well as a categorization by ESBL result. Patients with monomicrobial and polymicrobial will be summarized.

7.3 Baseline Microbiology

The bacterial pathogens identified from the baseline urine culture will be presented. In addition, the number and percentage of patients with mono-microbial and poly-microbial infections will be provided and also distribution of baseline pathogens by ESBL (positive/negative) and culture concentration will also be provided.

A listing will be provided that includes all baseline and post-baseline isolates obtained from specimens and whether or not the isolate is considered the pathogenic organism.

7.4 Prior and Concomitant Medications

All medications taken prior to the first dose of the study drug and through the TOC visit will be recorded on the source document. Concomitant antimicrobial medications will be summarized by WHODRUG (Version September 2014 or higher) ATC level 3 and generic medication name. Patients will be counted only once for an ATC class and generic medication name. Medications are considered concomitant if taken on or after the first dose of study drug, or if their stop date is unknown or marked as continuing.

The proportion of patients who receive, any antibiotic therapy with potential activity against any of the baseline uropathogens collected at screening between the time of the baseline culture and the EOT or TOC culture, will be summarized.

A listing will be provided of all antibacterial medications taken within 30 days prior to the first dose of study drug.

